4.3 Study Protocol and Data Acquisition

This is a prospective interventional study conducted on COPD patients (GOLD 2-4) under the Respiratory Unit, Department of Internal Medicine in UKMMC, who qualified both the inclusion and exclusion criteria. Beforehand, all potential subjects will undergo screening and survey to exclude any possible symptoms of COVID-19 disease. All eligible patients will be briefed about this study.

Subsequently, consent will be obtained from those who are agree to participate, either from the patient him/herself or their next-of-kin. The process of briefing and obtaining consent will be only done once the patient is stable. These processes will not in any way interfering with clinical evaluation, investigation, treatment and intervention done to the patient by the attending doctor. All of the consented patients will be given Aerobika® OPEP.

Prior to the initiation of Aerobika® OPEP device, baseline of IOS parameters, symptoms (using CAT score), lung function (using spirometry-FEV₁ and FVC), exercise capacity (using 6MWT) and exacerbation episodes of the past 6 months will be done and recorded in data collection sheet. All recruited patients will receive OPEP and trained to use for 10 minutes, 2 times per day ⁽³²⁾. Patients also will be emphasized that standard care for COPD management will be continued. An adherence sheet will also be provided to patients at which they can put crosses when they use the device as advised. They are encouraged to use Aerobika® immediately after using their inhalers in order to increase adherence of treatment.

Patients will be given phone call 2 days after they received Aerobika® as a reminder and also to ensure they are using it in a correct way. At week 12 and week 24 of Aerobika® OPEP usage, their IOS parameters, symptoms (using CAT score), lung function (using spirometry-FEV₁ and FVC), exercise capacity (using 6MWT) and exacerbation episodes will be reassessed. During clinic visit also, his/her standard management for COPD will be checked to ensure no change in the inhaler regime. Within the study period of 6 months, patient will be given follow-up phone calls every two to three weeks to ensure their adherence toward Aerobika®.

The entire clinical information will be retrieved from the medical department clerking chart and electronic health care record system of the studied patients. The follow-up data will be retrieved from the digital and written patient records to identify the frequency of exacerbation and any hospitalization. In cases where follow-up data are incomplete or missing, the patient or his/her next-of-kin will be called to obtain information on their condition, hospital admission, clinical and functional status.

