3.1.2 Secondary

- I. To evaluate improvement of symptoms using CAT score after 3 and 6 months.
- II. To evaluate improvement of lung function (using spirometry) and exercise capacity (using 6MWT) after 3 and 6 months.
- III. To evaluate moderate and severe exacerbation rates after Aerobika® OPEP device usage in 3 and 6 months.

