4.2.3 Sampling Population

This study will include patients diagnosed with COPD GOLD 2-4 attending the respiratory outpatient clinic UKMMC from June 2021 until November 2022. Demographic and clinical data will be collected. Patient will be followed-up at 3 and 6 months after intervention.

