4.2.4 Inclusion Criteria

- I. Age 40 years or older
- II. COPD diagnosed according to the GOLD guidelines: GOLD 2 - GOLD 4
- III. Stable COPD patients with mucus hyperproduction: coughed and brought up sputum “several days a week” (>2 days a week) or “almost every day” in the month prior to the study ⁽²⁵⁾
- IV. Patients who can perform IOS
- V. Patients who can perform spirometry

- VI. Patients who can perform 6MWT
- VII. Patients with small air disease as measured by IOS ($R5-R20 > 0.71 \text{ cmH}_2\text{O/L/sec}$)

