4.2.5 Exclusion Criteria

- I. COPD diagnosed according to the GOLD guidelines: GOLD 1
- II. Diagnosis of other chronic lung diseases: Asthma, Asthma-COPD Overlap, Interstitial Lung Disease, Bronchiectasis, Lung Cancer
- III. Patients with contraindication for spirometry: recent cardiac complications, major surgery ⁽³⁶⁾, severe advanced respiratory disease, or those with cognitively or neurologically impairment ⁽³⁷⁾
- IV. Patients not recommended for OPEP: neuromuscular weakness, recent facial, oral or skull surgery or trauma, recent oesophageal surgery, active haemoptysis, acute sinusitis, untreated pneumothorax, known or suspected tympanic membrane rupture or other middle ear pathology, overt right-sided heart failure ⁽²³⁾
- V. Patients with contraindication for 6MWT (**Table 1**)
- VI. Patient unable or unwilling to give informed consent
- VII. Change of inhaler during study period (will be dropped out from study)

Absolute and relative contraindications for field walking tests

Absolute	Relative
Acute myocardial infarction (3–5 days)	Left main coronary stenosis or its equivalent
Unstable angina	Moderate stenotic valvular heart disease
Uncontrolled arrhythmias causing symptoms or hemodynamic compromise	Severe untreated arterial hypertension at rest (200 mmHg systolic, 120 mmHg diastolic)
Syncope	Tachyarrhythmias or bradyarrhythmias
Active endocarditis	High-degree atrioventricular block
Acute myocarditis or pericarditis	Hypertrophic cardiomyopathy
Symptomatic severe aortic stenosis	Significant pulmonary hypertension
Uncontrolled heart failure	Advanced or complicated pregnancy
Acute pulmonary embolus or pulmonary infarction	Electrolyte abnormalities
Thrombosis of lower extremities	Orthopedic impairment that prevents walking
Suspected dissecting aneurysm	
Uncontrolled asthma	
Pulmonary oedema	
Room air S_{pO_2} at rest $\leq 85\%$ [#]	
Acute respiratory failure	
Acute noncardiopulmonary disorder that may affect exercise performance or be aggravated by exercise (i.e. infection, renal failure, thyrotoxicosis)	
Mental impairment leading to inability to cooperate	

Table 1: Absolute and relative contraindications for field walking tests ⁽³⁸⁾

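### Objective III compares exacerbation rates with a 6-month baseline, but the follow-up window, time denominator and severity grading are not stated

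*Combined protocol and SAP*

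**What the plan says.** Section 3.1.2, objective III: "To evaluate moderate and severe exacerbation rates after Aerobika® OPEP device usage in 3 and 6 months". Section 4.5 states that there is no untreated arm and that every parameter will be compared between baseline and the two follow-up visits, so each patient's baseline is the only reference.

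For baseline, section 4.3 has "exacerbation episodes of the past 6 months will be done and recorded in data collection sheet", and the Chapter 9 data sheet has a field with the same 6-month period. For weeks 12 and 24, section 4.3 says only "exercise capacity (using 6MWT) and exacerbation episodes will be reassessed". It also plans to retrieve the frequency of exacerbations from patient records, without naming a period. Section 4.2.3 describes the schedule as "Patient will be followed-up at 3 and 6 months after intervention".

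The Chapter 9 grid has a single exacerbation row with cells for weeks 0, 12 and 24. It gives no window, no event dates and no severity grade. Section 4.4.2 defines mild, moderate and severe events but does not define a rate.

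Section 4.6 (data collection pathway) has no readable content, so this point is limited to the text that can be read.

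**The concern.** A count of events grows with the time over which it is collected. The baseline period is fixed at 6 months, and the month-3 visit falls only 12 weeks after device start. Unless the plan says how the two are put on the same scale, the comparison can show a change that comes from window length alone. With a concurrent control arm both groups would share the follow-up window and the mismatch would largely cancel. Here nothing cancels it, and it would be read as a device effect.

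The second gap is in the data. The objective covers moderate and severe events only. One ungraded entry per visit cannot separate these from the mild, self-managed events that section 4.4.2 also defines. The sheet as drawn therefore does not yield the endpoint on its own.

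At stake is whether two analysts following this plan would report the same answer for objective III, particularly at month 3.

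**Working it through.** The plan gives no figure for exacerbation rates, so there is none to reproduce. The check is how far each possible reading moves the result when the true rate has not changed.

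**Inputs**
- Baseline window: 6 months (section 4.3 and Chapter 9), or 365.25/2 = 182.6 days.
- Follow-up visits: weeks 12 and 24 (section 4.3), or 84 and 168 days. Sections 3.1.2 and 4.2.3 call them 3 and 6 months.
- Follow-up window: not stated.
- Assumptions: a constant event rate, and the 6-month baseline count as comparator. No particular rate or test has to be assumed.

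**Formula.** Expected count = rate × window. At an unchanged rate, follow-up count / baseline count = follow-up window / baseline window, and the apparent fall is 1 minus that ratio.

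| Reading of the follow-up entry | Month 3 | Month 6 |
|---|---|---|
| Raw count since device start, cumulative | 3/6 = 0.50, fall 50%; 84/182.6 = 0.460, fall 54% | 6/6 = 1.00, fall 0%; 168/182.6 = 0.920, fall 8% |
| Raw count, restarting at week 12 | fall 50-54%, as above | 3/6 or 84/182.6 again, fall 50-54% |
| 6-month look-back from the visit | 182.6/182.6 = 1.00, fall 0% | 182.6/182.6 = 1.00, fall 0% |
| Events per unit time since device start | ratio 1.00 | ratio 1.00 |

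**Break-even.** On a raw count since device start, the true rate would have to rise 1/0.50 = 2.0-fold to 1/0.460 = 2.17-fold before the month-3 count stopped looking lower than baseline.

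**Cost of the look-back reading.** At week 12, 182.6 − 84 = 98.6 days, about 14 weeks, precede device use. That is 98.6/182.6 = 54% of the window. If the device multiplies the rate by r, the expected ratio is 0.54 + 0.46r, so the observed relative change is 0.46(r − 1). Less than half of any true change would be seen. At week 24 the overlap is 182.6 − 168 = 14.6 days, or 8% of the window.

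**Range.** The gap between 50% and 54%, and between 0% and 8%, is only calendar conversion. The protocol uses week 12 and month 3 interchangeably, and on that convention the figures are 50% and 0%.

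**The case against.** The strongest reply is that no section plans a comparison of raw counts. Objective III says rates, which normally implies division by time, and the sentence in section 4.5 about comparing all parameters is general wording in a sample-size section. A 6-month baseline beside "Within the study period of 6 months" also suggests that matched periods were intended. This stands as far as it goes: with events per unit time since device start, the window artefact is zero. But the rate is not defined in the readable text.

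A reader might infer that the plan builds in a false halving of exacerbations in the device's favour. The documents do not support that. It needs three conditions together: raw counts, a week-12 entry that starts at week 0, and the 6-month count as comparator. The follow-up wording also permits a repeated 6-month look-back, which gives no artefactual fall and pulls any change towards zero. The comparator is not certain either, because the grid has its own week-0 cell, with no stated window, apart from the 6-month field.

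It might be said that objective III already sets windows of 0-3 and 0-6 months. The primary objective uses the same phrase for assessment times. If windows were meant, the month-3 mismatch with baseline becomes explicit.

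A reader might also infer that severity can never be recovered. That goes too far. Section 4.3 plans record retrieval and section 4.4.2 supplies the grades, so much of it may be reconstructed later. Mild, self-managed events are the least likely to appear in records, which is a reason to log events prospectively.

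Finally, "Stable COPD patients with mucus hyperproduction" are recruited. A spell free of events before entry would lower the baseline count and shrink the 50%. The text gives no duration for stability, so no figure can be put on this.

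**Conclusion.** The point holds as an undefined endpoint with a large conditional consequence. Baseline has a 6-month window. The week-12 and week-24 counts have no stated window or denominator, and the sheet cannot separate mild from moderate or severe events. At a constant rate, the choice among permitted readings moves the month-3 result from no change to an apparent fall of about 50%, or dilutes a true change to less than half its size. Month 6 is affected little unless the count restarts at week 12.

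Dividing by person-time removes the window artefact only. The comparison remains an uncontrolled before-and-after one.

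The matter is confined to one secondary objective. The primary oscillometry endpoint does not depend on a counting window, and the sample size of 34 (48 with the 40% addition) was set on a standardised paired difference, not on exacerbations. It should be corrected, but it does not threaten the main result.

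**What to change.** - **Define the rate in one sentence:** moderate and severe events (section 4.4.2) from device start to each visit, divided by the person-time observed.
- **Replace the single grid row with a short event log:** one line per event with its date and severity grade, before and after device start. Adding columns to the three-visit grid would not hold several events per patient.
- **Use the same sources for both periods.** Section 4.3 already plans record retrieval and telephone contact when data are missing.
- **Count early leavers up to the date of leaving.** Patients removed under section 4.2.5 item VII (inhaler change) should contribute their events and time until then.
- **Report both visits on the per-time scale.** The cumulative 24-week result against the 6-month baseline is the closest match in length. Month 3 should be shown on the same scale, not as a raw count.

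The cost is one added definition, an event log and slightly more record abstraction. No extra visits or patients are needed.

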4.4 Operational Terms Definition

4.4.1 Chronic Obstructive Pulmonary Disease (COPD)

Chronic obstructive pulmonary disease (COPD) is a common, preventable and treatable disease that is characterized by persistent respiratory symptoms and airflow limitation that is due to airway and/or alveolar abnormalities usually caused by significant exposure to noxious particles or gases ⁽³⁾

4.4.2 COPD Exacerbation

COPD exacerbation is defined as:

- I. Mild COPD exacerbation was defined as worsening of symptoms that were self-managed (by measures such as an increase in salbutamol use) and resolved without systemic corticosteroids or antibiotics
- II. Moderate exacerbation if treated with systemic steroids and/or antibiotics
- III. A severe exacerbation if hospitalisation is required for treatment of exacerbation or admission to emergency > 24 hours ⁽³⁹⁾

4.4.3 COPD Staging based on GOLD

GOLD STAGE	SEVERITY	FEV ₁
Stage 1	Mild	FEV ₁ > 80% predicted
Stage 2	Moderate	50% ≤ FEV ₁ < 80% predicted
Stage 3	Severe	30% ≤ FEV ₁ < 50% predicted
Stage 4	Very severe	FEV ₁ < 30% predicted.

Table 2: Classification of Airflow Limitation Severity (Based on Post-Bronchodilator FEV₁)⁽³⁾

4.5 Sample Size

[figure not shown]
According to Cohen's d formula, Cohen suggested that effect size of 0.2, 0.5 and 0.8 as small, medium and large effect size respectively. Effect sizes are the most important outcome at which the researchers want to know whether an intervention or experimental manipulation has an effect greater than zero, or (when it is obvious an effect exists) how big the effect is⁽⁴⁰⁾. In our study, we aim to have a medium effect size with the usage of Aerobika®. An effect size of 0.5 is described as medium and is 'large enough to be visible to the naked eye'⁽⁴¹⁾.

By using online statistical calculator apps; Sample Size Calculator for Comparing Paired Differences, this study would require a sample size of 34 to achieve a power of 80% and a level of significance of 5% for detecting an effect size of 0.5 paired differences (Dhand, N. K., & Khatkar, M. S. (2014). Statulator: An online statistical calculator. Sample Size Calculator for Comparing Two Paired Means. <http://statulator.com/SampleSize/ss2PM.html>.

Additional of 40% samples is recruited to avoid subject consent withdrawal, drop out, or missing data. Therefore, a total of minimum 48 patients will be recruited for this study. However, we aim to recruit 60 patients as we were sponsored 60 units of Aerobika® OPEP.

The outcomes of this study will be evaluated on all patients by comparing all the parameters during baseline and at 3- and 6-months follow-up after using Aerobika®. There will be no non-interventional arm as the sample size will become bigger. During the COVID-19 pandemic era, we would like to reduce the exposure towards those performing respiratory tests. The other limitations as well with larger sample size are budget and time constraint.

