4.2 Study Design

4.2.1 Period of Study

The study will be conducted from June 2021 to November 2022 after receiving approval by the research ethics committee.

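### Does the 40% add-on leave the minimum of 48 patients too small to protect 80% power?

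*Combined protocol and SAP*

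**What the plan says.** All references are to the combined protocol and SAP. Section 4.5 (Sample Size) rests on a standardised paired difference of 0.5: "this study would require a sample size of 34 to achieve a power of 80" per cent and "a level of significance of 5% for detecting an effect size of 0.5 paired differences". It then inflates: "Additional of 40% samples is recruited to avoid subject consent withdrawal, drop out, or missing data. Therefore, a total of minimum 48 patients". The next sentence raises the figure: "However, we aim to recruit 60 patients as we were sponsored 60 units of Aerobika® OPEP".

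The budget in Chapter 6 fits the higher figure. Filters, mouthpieces and technician fees are each costed at 180, which is 60 patients at three visits (weeks 0, 12 and 24).

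Two other places bear on losses. Section 4.2.5 lists one reason for removal after entry: "Change of inhaler during study period (will be dropped out from study". On dates, section 4.2.1 says "The study will be conducted from June 2021 to November 2022 after receiving approval by the research ethics committee", and section 4.2.3 includes patients "attending the respiratory outpatient clinic UKMMC from June 2021 until November 2022", with follow-up at 3 and 6 months.

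**The concern.** The purpose of the 40% is to guard against withdrawal, dropout and missing data. A reader may therefore take it as the loss the study can absorb. On that reading the wrong formula was used: to keep n evaluable patients after a loss fraction L, one recruits n/(1 − L), not n(1 + L). A study that stopped at 48 and lost 40% would have 28 pairs, too few for the stated power.

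The plan gives no expected loss rate, so the adequacy of 48 cannot be judged directly. Removal after an inhaler change adds losses at an unstated rate. The telephone contact in section 4.3 can recover admissions and clinical status, but not an IOS reading, so a missed IOS visit is a lost pair for the primary objective.

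The dates raise a second doubt. If patients could enter until the end of November 2022 and the study closed then, late entrants would have no week-24 visit and would use up part of the same allowance.

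**Working it through.** **Inputs.** Effect size 0.5, 5% significance, 80% power, 34 pairs, 40% add-on, minimum 48 and target 60 (section 4.5); visits at weeks 12 and 24 (section 4.3); dates June 2021 to November 2022 (sections 4.2.1 and 4.2.3). Sidedness is not stated; two-sided is assumed because it reproduces the 34. No loss rate is given, so a range of 20% to 40% is shown.

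**1. The plan's 34.** The normal approximation gives ((1.960 + 0.842)/0.5)² = 31.4. Adding 1.960²/2 = 1.92 gives 33.3, so 34. With the noncentral t distribution, 34 pairs give 80.8% power and 33 give 79.5%. The figure reproduces. A one-sided test would need about 25 and does not match.

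**2. The plan's 48.** 34 × 1.4 = 47.6, so 48. It reproduces as an add-on.

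**3. The alternative reading.** If 40% were the loss rate: 34/(1 − 0.40) = 56.7, so 57.

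**4. Largest loss that leaves 34 pairs, (N − 34)/N.**
- N = 48: 14/48 = 29.2%
- N = 57: 23/57 = 40.4%
- N = 60: 26/60 = 43.3%

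**5. Pairs left, rounded down, with power at effect size 0.5.**

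| Recruited | 20% lost | 30% lost | 40% lost |
|---|---|---|---|
| 48 | 38 (85.1%) | 33 (79.5%) | 28 (72.3%) |
| 57 | 45 (90.7%) | 39 (86.1%) | 34 (80.8%) |
| 60 | 48 (92.4%) | 42 (88.6%) | 36 (83.1%) |

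At 60, power stays above 80% across the range. At 48 it is 0.5 points short at 30% loss and materially short only towards 40%.

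**6. Dates, as a hypothetical.** Assume even accrual from 1 June 2021 to 30 November 2022 (548 days) and a hard data cut-off on the last day.
- Week 24: 30 November less 168 days is 15 June 2022, day 380. 380/548 = 69.3% of recruits could reach the visit: 48 × 0.693 = 33.3 patients, or 60 × 0.693 = 41.6. Forty pairs give 86.9% power and 42 give 88.6%, so the target of 60 stays clear of 80%. A further loss of 1 − 34/41.6 = 18.3% would bring it to 34.
- Week 12: 30 November less 84 days is 7 September 2022, day 464. 464/548 = 84.7%, which is 40.6 of 48 or 50.8 of 60. Both exceed 34 before other losses.

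**The case for a change.** The strongest case for a change is that 48 is the only recruitment figure derived from the power calculation and the only one called a minimum, while 60 reflects how many devices were donated. A team that stopped at 48 would be within its protocol. It would then have no margin beyond 29%, in a 24-week study of GOLD 2–4 patients that removes anyone whose inhaler changes. Restating the minimum as 57 would cost nothing, because it lies below the target, the device supply and the budgeted tests.

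Part of this stands. The plan should ideally name an expected loss rate, and a reader who takes 48 as proof against a 40% loss is mistaken.

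The rest does not carry a change. The reason for choosing 60 does not alter the protection it gives. Because 57 lies below 60, restating the minimum would add no patient, device or test. Removal after an inhaler change is a form of dropout, which the add-on names among the losses it covers. No figure in the documents suggests losses above 29%.

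On timing, the two windows do coincide, and a stated last entry date would be clearer. But section 4.2.1 places the whole conduct of the study inside its window, and the natural reading is that follow-up falls there too, so entry stops earlier. The bars of the Gantt chart and the content of the data collection pathway (section 4.6), which may settle this, are not visible in the text reviewed, so their absence cannot be held against the plan. Either remedy also has a price. Closing entry on 15 June 2022 raises the accrual needed for 60 patients from 60/18 = 3.3 to 60/12.5 = 4.8 per month. Waiting for late entrants could put the last week-24 visit at 17 May 2023.

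**Conclusion.** No change is needed. The 34 and the 48 are both right as written, and 57 follows only if the 40% is taken to be a loss rate, which section 4.5 does not say. At the planned 60, the study keeps at least 34 pairs up to a 43% loss and has 83% power at 40% loss. The exposure is confined to recruitment ending near 48 with losses above 29%. Just past that point power is 79.5%, and it reaches 72% only at a full 40% loss. The unstated loss rate is missing detail that does not alter what the team will do. The date overlap is an ambiguity that ordinary trial conduct resolves: a patient who cannot complete follow-up within the study is either not enrolled or is waited for.

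This rests on a two-sided paired t-test at effect size 0.5, on recruitment being pursued to the stated 60, and on total losses, including any missed week-24 visits, staying at or below 43%.
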